completed treatment. ***Following randomization of the schools to the intervention, there will be three waves of implementation: Wave 1 (1 school in 2019), Wave 2 (2 schools in 2019-2020), and Wave 3 (2 schools in 2020-2021).*** The 5 schools on the Fort Peck Reservation will be the clusters that are randomized to *NIE*. *NIE* will take approximately 40 weeks, or 3 quarters, to implement. The first observation period (Q4 of Year 2) provides baseline measurements for all respondents drawn from every cluster. The cluster is then surveyed at 3, 9, and 12 months for the students in the cluster once they have begun participation in the intervention, and at 9 and 12 months for the parents/legal guardians in the cluster once they have begun participation in the intervention. Following completion of the intervention across all clusters, we will conduct the quantitative analysis. The SWD allows us to control for the effect of time and ensure that the full AI population of schools at Fort Peck receives *NIE*. The systems-level component of *NIE* will be implemented reservation-wide rather than school-wide during Years 2 to 4 of *NIE* as the SWD is rolled out. The systems level component will be measured and analyzed qualitatively.

**2.3.6 Trial Timeline.** The timeline for *NIE* is: Year 1-Refine, tailor, and finalize the components of *NIE* with the CAB by reviewing our current quantitative and qualitative data from Fort Peck and by talking with elders

[figure not shown]

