### SECTION 3: ANALYSIS PLAN

**3.1.1 Power analysis.** Sample size requirements were calculated taking into account a unique design effect for the SWD, such that  $N_{sw} = Nu \times DE_{sw}$  (where  $Nu$  is the total number of students needed to detect the treatment effect with a power of 80% and a significance level of 0.05, uncorrected for cluster and repeated measurements). The design effect was calculated as:

$$DE_{sw} = \frac{1 + \rho(ktn + bn - 1)}{1 + \rho\left(\frac{1}{2}ktn + bn - 1\right)} \times \frac{3(1 - \rho)}{2t(k - \frac{1}{k})}$$

where  $k$  is the number of steps,  $n$  is the expected number of students per cluster,  $b$  is the number of baseline measurements,  $t$  is the number of measurements after each step, and  $\rho$  is the intra-class correlation coefficient, estimated to be 0.016 based on findings reported by Kaufman et al. With an  $\rho$  of 0.05, power of 0.8,  $Nu = 292$ ,  $DE_{sw} = 1.3273$ , and the expectation of 15% attrition during the study, a sample size of 456 will allow the detection of a 0.14 increase in the proportion of condom use relative to the frequency of sexual intercourse from baseline to the 12-month observation period hypothesized under Aim 2.

**3.1.2 Missing data.** Attrition is likely to covary with truancy, suggesting a missing data mechanism that is not missing at random (NMAR). To address this, a dropout variable  $D_i$  will be developed for each individual across the 4 observation periods, where  $D_i=k$  for dropout between the  $(k-1)$  and  $k^{\text{th}}$  occasion. A model of the probability of dropout, where

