$\log \left\{ \frac{\Pr(D_i=k \mid D_i \geq k, Y_{i1}, \dots, Y_{ik})}{\Pr(D_i>k \mid D_i > k, Y_{i1}, \dots, Y_{ik})} \right\} = \theta_1 + \theta_2 Y_{ik-1} + \theta_3 Y_{ik}$  presumes that  $\theta_3 \neq 0$  for the NMAR mechanism. Missing data will be examined using multiple imputation, where missing values are replaced by a set of  $m$  plausible values using a propensity scoring sequence to generate a single estimate of the parameters of interest. Observations will first be grouped on the basis of propensity score similarity, then individuals with missing values will be randomly matched to those with observed values, and finally missing values will be randomly selected with replacement from the random sample of observed values. This sequence will be repeated sequentially starting at the 3-month follow-up observation through the 12-month follow-up observation, and the entire propensity scoring and time imputation sequence(s) will be repeated at minimum across 2:5 datasets ( $m$ ) to estimate  $\bar{\beta} = \frac{1}{m} \sum_{k=1}^m \hat{\beta}^{(k)}$ . Sensitivity analyses will also be used to assess the robustness of primary results attributable to missing data by examining imputed and nonimputed data.

**3.1.3 Dose.** The treatment dose is the number of intervention components delivered to the individual student, accounting for individual students' attendance and participation. This will be tracked using the fidelity log, staff field notes, and the CAB meeting. A count, nominal, or weighted percentage will be used to represent dose pending analysis of the dose frequency distribution.

**3.1.4 Baseline data analysis.** Baseline data will first be analyzed to determine whether demographic and SRH variables vary relative to school (cluster). The psychometric properties of scales will be explored, and confirmatory factor analyses (CFA) for scales will be conducted. Finally, structural equation models (SEM) will

Woertman W et al. Stepped wedge designs could reduce the required sample size in cluster randomized trials. *J Clin Epidemiol*. July 2013;66(7):752-758.

Kaufman C et al. Effectiveness of Circle of Life, an HIV-preventive intervention for American Indian middle school youths. *Am J Public Health*. June 2014; 104(6):e106-e112.

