$Y_{ijl} = \mu + \beta_j + \theta X_{ij} + u_i + e_{ijl}$ , and where  $u_i \sim N(0, \sigma_u^2)$ ;  $e_{ijl} \sim N(0, \sigma_e^2)$ , with  $\beta_j$ =the fixed effect of time,  $X_{ij}$ =intervention (0,1 or dose representation),  $\theta$  =intervention effect,  $u_i$ =random effect for cluster, and  $e_{ijl}$ =residual for  $i$  clusters,  $j$  time periods, and  $l$  adolescents.  $Y_{ijl}$  will be modeled for SRH outcomes and interpreted in terms of a contrast of the log odds of response relative to AI youths with similar values for unobserved random effects. In order to test for changes in the tertiary outcomes, we will specify  $Y_{ijl}$  as continuous response outcomes. STATA statistical software will be used to conduct GLMMs. However, SAS will be used if more complex specification of the intraclass correlation becomes necessary.

**3.1.6 Analysis of focus group data.** Focus group data will be transcribed and coded using a partially inductive procedure. First, all transcript data will be open coded (line-by-line coding). The open codes will be pre-sorted based on whether participants are responding to acceptability or fidelity prompts. Within each implementation domain, axial codes will be developed to group the open codes, and the team will meet to discuss how axial codes saturate the pre-defined acceptability and fidelity categories. Transcripts will be coded using Atlas.ti software.

**3.2 Qualitative Data Analysis.** The systems level component and the FAS evaluation component of N/E will be analyzed using content analysis. Common themes will be identified from the two respective sets of data collection instruments. Coding will proceed in stages. A topical indexing scheme will be developed with input from the community advisory board members to identify the text pertaining to particular topics relevant to the systems level and FAS components of N/E. The software program, Atlis.ti will be used to construct and organize a topical indexing system of codes identifying sections of text that capture the central concepts of interests. Then, content coding will be developed by the research team with advice from the community

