H1: AI youth who participate in N/E will demonstrate increased condom use at 3, 9, and 12 months. (12 months will be used in the Primary Outcome analysis; 3 and 9 months will be used in the Secondary Outcomes analysis.) H2: AI youth who participate in N/E will demonstrate increased use of other birth control at 3, 9, and 12 months. They also will demonstrate a decrease in sexual risk behaviors as measured by reduced number of sex partners, delayed onset of sexual intercourse, and decreased substance use during sex, at 3, 9, and 12 months. (Secondary Outcomes) H3: N/E parents/legal guardians and youth will demonstrate significantly increased communication about topics related to SRH at 3, 9, and 12 months. AI youth who participate in the cultural mentoring program will demonstrate significantly increased understanding of cultural values related to traditional AI beliefs regarding SRH at 3, 9, and 12 months. And AI youth who participate in N/E will report significantly increased use of SRH services at 3, 9, and 12 months as a result of improved coordination among education, health care, and social service agencies on the Fort Peck Reservation. (Tertiary Outcomes) AIM 3: Evaluate the fidelity and acceptability of N/E. N/E's fidelity and acceptability will be evaluated using qualitative methods, including focus groups, activity logs, and staff field notes and meetings.

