## Outcome Measures

### Primary Outcome Measure:

1. Change in condom use during sexual intercourse at 3 months, 9 months and 12 months

Change in condom use during sexual intercourse will be measured as proportion of condom use during sexual intercourse will be measured using 2 items (number of times condom used relative to number of times had sexual intercourse).

[Time Frame: 3 months, 9 months and 12 months]

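### The model's single intervention term may be 0/1 or attendance dose, with neither made primary, and Section 3 does not carry out the 12-month primary analysis named for H1

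*Combined protocol and SAP*

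**What the plan says.** **Coding of the intervention.** Section 3, under 3.1.5 Generalized linear mixed-effects models, gives one model for all Aim 2 hypotheses: Y_ijl = μ + β_j + θX_ij + u_i + e_ijl, for cluster i, period j and adolescent l. X_ij is "intervention (0,1 or dose representation". Section 3.1.3 defines the alternative: "The treatment dose is the number of intervention components delivered to the individual student", allowing for attendance and participation. It adds: "A count, nominal, or weighted percentage will be used to represent dose pending analysis of the dose frequency distribution". No section names the 0/1 coding or an as-assigned analysis as primary, or dose as secondary.

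**Attendance and missing outcomes.** Section 3.1.2 states: "Attrition is likely to covary with truancy, suggesting a missing data mechanism that is not missing at random (NMAR").

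**Time point.** The power analysis (3.1.1) concerns a 0.14 increase "from baseline to the 12-month observation period hypothesized under Aim 2". H1 in the registration record (Detailed Description), repeated in the progress report at 8.1, reads: "12 months will be used in the Primary Outcome analysis; 3 and 9 months will be used in the Secondary Outcomes analysis". The same registration record gives the primary outcome measure as "Change in condom use during sexual intercourse at 3 months, 9 months and 12 months". The model paragraph has one θ, no term for time since start, and no restriction on which visits enter the primary fit.

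**The concern.** Schools are randomised; attendance is not. With X = 0/1, θ compares school-periods after the randomised start with school-periods before it. With X = dose, treated students are also compared with one another by how much they attended. Students who attend more may differ in condom use for reasons unrelated to the programme. Because the plan offers both codings for the same term, and leaves the form of dose open until it has been examined, a headline result that complies with the plan could be an attendance comparison with a coding chosen from the data.

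The second matter is narrower. The 12-month time point has been chosen, but the model paragraph does not implement it. One constant θ fitted to every follow-up estimates an average over visits, two of which H1 calls secondary.

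**Working it through.** **The plan's own figure.** 292 × 1.3273 = 387.57, and 387.57 / 0.85 = 455.97, so 456 is reproduced. It is not in dispute here. The SD implied by 292 students in total, a difference of 0.14, 80% power and two-sided 0.05 is 0.14 × √(292/4) / (1.960 + 0.842) = 0.427. I also use 0.5, the largest SD possible for an outcome between 0 and 1.

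**Dose.**
1. Dose belongs to student l, but X_ij is indexed only by school and period. The printed formula cannot hold it without becoming X_ijl.
2. Write dose as T_ij × s_l, where T is the school's randomised status and s is the student's attendance share. Suppose θ = 0 but s is correlated with condom use. Within a treated school-period, the covariance of dose with the outcome equals the covariance of s with the outcome, which is not zero. Control records all have dose 0 and cannot reveal that covariance. T itself does not vary within a school-period, so 0/1 coding is unaffected.
3. The documents give no attendance–outcome correlation, so the size must be assumed. For illustration, take mean attendance 0.7, SD 0.15–0.30, within-student correlation 0.3–0.5 and a student random intercept, over yearly wave starts and one shorter schedule. The false-positive rate of the dose coefficient is then 0.05–0.09 at correlation 0.05 and 0.06–0.21 at correlation 0.1. With X = 0/1 it stays at or below 0.05, with no bias.

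**What the single θ estimates.** I used generalised least squares on school-by-survey means, on the linear scale.
- *Inputs:* five schools in waves of 1, 2 and 2 (2.3.5); a baseline survey and surveys at 3, 9 and 12 months; 456 × 0.85 / 5 = 77.5 students per school per survey; ICC ρ = 0.016 (3.1.1).
- *Assumed:* waiting schools are surveyed at every round, and no school is surveyed after its month 12.
- *Estimator:* θ̂ is the last element of (X′V⁻¹X)⁻¹X′V⁻¹Y, with V = σ²[ρZZ′ + ((1 − ρ)/77.5)I], where Z marks schools.

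Yearly starts (months 0/12/24) give 5 + 3 + 2×6 + 2×9 = 38 cells, and θ's weights on 3, 9 and 12 months are 0.333 each. September starts at 0/0/12 and 0/12/12 also give 1/3 each, because within any school year the same schools are treated and waiting at all three rounds.

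θ is therefore the three-visit average. For an assumed build-up of 0.035, 0.105 and 0.14, θ = 0.280/3 = 0.093 against 0.14 at 12 months. For an assumed fade of 0.14, 0.10 and 0.05, θ = 0.290/3 = 0.097 against 0.05. A constant effect is not an obvious assumption. Table 1 delivers Native Stand twice a month, so about six sessions precede the 3-month survey, while the condom and birth-control session is the tenth, in about month 5 if the listed order is followed.

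**Precision of the 12-month effect, yearly starts.** Power = Φ(0.14/SE − 1.960).

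| | SD 0.427 | SD 0.5 |
|---|---|---|
| SE, pooled θ | 0.0290 | 0.0340 |
| SE, 12-month term | 0.0412 | 0.0483 |
| Power, 12-month term | 0.92 | 0.83 |

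The SE ratio is 0.0412/0.0290 = 1.42. Fitting control plus 12-month records only gives an SE of 0.0415 at SD 0.427, practically the same.

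**The case against.** **That 12 months is already settled.** This largely stands. H1 allocates visits to analyses, and applied to the Section 3 model it could mean fitting control and 12-month records only, in which case θ is the 12-month effect. A reader might infer that the plan never chose a primary time point; the registration record and progress report show that it did. What remains is that Section 3 does not repeat the rule and the registered primary outcome measure conflicts with it.

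**That 0/1 is the natural default.** The design-effect formula presumes on/off crossover, and a difference of 0.14 suits 0/1 coding. That suggests intent, but it does not remove the printed alternative.

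**That the dose bias could be large.** A reader might infer a very high false-positive rate by fitting student-level dose with no within-student correlation. The documents do not support that reading. The printed term has no student index, and 3.1.5 says the model allows autocorrelation within individuals. The rates shown above are illustrations on assumed inputs and do not carry the point.

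**That the 3-month visit might dominate θ.** This needs Wave 2 to start partway through the school year. Delivery over the 9-month school year (2.3.4), and Wave 1 surveys in December, May/June and September with the later waves following the same pattern (4.1), point to September starts, for which the weights are equal.

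**That waiting schools may not be surveyed.** Section 2.3.5 describes follow-up surveys only after a cluster has begun. On a literal reading with separate calendar-period effects, θ is not identified (rank 10 for 11 columns). The design figure is not shown, so I do not rest the point on this.

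**Conclusion.** The dose point holds on the text alone. The randomised coding is not made primary, the alternative is a post-randomisation attendance measure coded after it has been inspected, and the plan's own view of truancy and attrition makes an attendance–outcome link plausible. The size and direction of any bias are unknown from the documents.

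The 12-month point holds as an inconsistency between Section 3 and H1, and between H1 and the registered primary outcome measure. If all follow-ups are fitted, θ equals the 12-month effect only if the effect is constant or the three-visit average happens to match it. The weights of 1/3 assume September starts and surveys of waiting schools.

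The power figures of 0.92 and 0.83 apply to yearly starts and are upper limits. They use a linear normal approximation with five schools and let every retained student contribute, although survey items 5.5 and 5.6 define the proportion only for students reporting sex in the past month. The schedule itself needs confirming. Sections 2.3.6 and 4.1 fit yearly starts, but 2.3.5 gives "Wave 1 (1 school in 2019), Wave 2 (2 schools in 2019-2020), and Wave 3 (2 schools in 2020-2021") and the registration record anticipates primary completion in November 2021. Yearly starts from September 2019 would put Wave 3's 12-month survey in September 2022. On a 0/0/12 schedule, 12-month power by the same method is about 0.72 (SD 0.427) or 0.59 (SD 0.5).

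This should be corrected before analysis.

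**What to change.** 1. In Section 3, state that the primary analysis uses X = 0/1 randomised school status. Make dose secondary or exploratory, with one coding fixed in advance and a student index (X_ijl). This costs only wording.
2. In the model paragraph, repeat the H1 rule. Either fit control plus 12-month records, or use separate 3-, 9- and 12-month terms with the 12-month term primary and the other two secondary. On yearly starts this costs the factor of about 1.4 in standard error shown above.
3. Align the registered primary outcome measure with H1, which needs a registry update.
4. Reconcile the wave dates in 2.3.5, 2.3.6, 4.1 and the registration record, state whether waiting schools are surveyed at each round, and restate power for the 12-month contrast on the confirmed schedule.

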**2.3.2 Study Aims.**

- **AIM 1** begins with a year of formative work to refine and tailor the components of N/E. Our community advisory board and the Fort Peck-based and MSU-based research team will design culturally appropriate adaptations for N/E's 4 levels.
- **AIM 2** tests the efficacy of N/E using a cluster-randomized stepped-wedge design (SWD), in which the 5 high schools that Fort Peck youth attend are randomized into the intervention 1 at a time. N/E's primary outcome is increased condom use during sexual intercourse. Secondary outcomes are delayed onset of sexual intercourse, number of sex partners, frequency of sexual intercourse, pregnancy history, consistent use of birth control during sexual intercourse, and whether alcohol and/or other drugs are used during sexual intercourse. Tertiary outcomes are increased parent/legal guardian-child communication about SRH topics, increased understanding of cultural values related to traditional AI beliefs regarding SRH, and increased use of SRH services. Quantitative data collection includes: student surveys at baseline, 3, 9 and 12 months; parent/legal guardian surveys at baseline, 9 and 12 months. Qualitative data collection includes SRH service provider discussion groups at baseline and thereafter once a year over the 5-year study, with logs to track coordination and implementation at baseline and 3, 6, 9 and 12 months.
- **AIM 3** will evaluate the fidelity and acceptability of N/E with focus groups, activity logs, and staff meeting notes and staff field notes.

Our **long-term goal** is to produce a toolkit, including curriculum manuals, an SRH cultural mentoring program, and specific systems-level actions suitable for replication in other tribal communities. The **public health impact** is the prevention of STIs, HIV, HCV, and teen pregnancies in AI youth resulting in reduced sexual and reproductive health disparities and improved health in AI families and communities.

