be developed based on the multi-level components derived from the Ecological Systems Theory model

upon with the N/E was built. CFAs and SEMs will be conducted using Mplus software.

**3.1.5 Randomization of schools.** The 5 schools that AI youth from Fort Peck attend are the clusters to be randomized into the intervention, with all schools eventually being randomized to the intervention. Students and their parents/legal guardians will be recruited for baseline participation prior to randomization of the sites. Schools will be randomized to the intervention following baseline data collection using a single sequence random assignment to clusters that will determine order of intervention receipt.

**3.1.5 Generalized linear mixed-effects models.** To test for effectiveness of the *NIE* intervention across all hypotheses under Aim 2, the generalized linear mixed-effects models (GLMM) will be used to model binary primary and secondary outcomes (condom use under H1, condom use and other sexual risks under H2) and continuous tertiary outcomes (H3) in the data. The GLMM allows for individual-level binary and continuous responses to be modeled, key covariates to be controlled for, the specification of autocorrelation within individuals, and clustering by school. The GLMM is also the most frequently employed analytic method to adjust for the longitudinal nature of SWDs, and it was chosen over the Generalized Estimating Equations (GEEs) because GEEs show inflated Type 1 error rates when the number of clusters is small, as is the case with the number of schools at Fort Peck. Hussey and Hughes proposed a mixed-effects regression approach for the SWD-CRT design, where:

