Exclusion criteria are minimal due to the value the CAB places on inclusion in N/E's program implementation. Exclusion criteria include 1) not meeting the aforementioned inclusion criteria, and 2) having a physical or cognitive impairment that would impede the student's understanding of and participation in the content of Native Stand, Native Voices, and the cultural mentoring program. Study-enrolled students must agree at the outset to participate in Native Stand, Native Voices, and the cultural mentoring program, and agree to complete the survey at baseline and at 3, 9, and 12 months during and shortly after their cluster's program. Parents/legal guardians must also agree to participate in Native Voices and complete the parent/legal guardian survey at baseline and at 9 and 12 months. No persons will be coerced to engage in any study activity, and anyone may refuse to participate at any time. After written consent and assent are obtained from the parents/legal guardians and their children, respectively, they will be enrolled in the study. For inclusion in the systems-level component of the study, only those staff members who sit on the Epi Team as representatives of their respective agencies are eligible. Written informed consent will be obtained from the head of each agency represented on the Epi Team and the staff member participating in the Epi Team.

If at any point in the study a student discloses abuse, they will be referred to the appropriate person or organization. For example, a research participant who is under the age of 18 and in school who discloses that he or she is being abused at home will be referred to the counselors in the school for assistance, with the possibility of joint reporting to Child Protective Services. Students will be informed during the informed consent process that any abuse they may disclose will be reported, since the members of the research team and the interviewers are mandated reporters.

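### The analysis equation has no student term although each student is surveyed four times, so the standard error of the intervention effect is miscalibrated (too wide with 0/1 exposure)

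*Combined protocol and SAP*

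**What the plan says.** Section 3.1.5 (Generalized linear mixed-effects models) gives one equation: Y_ijl = μ + β_j + θX_ij + u_i + e_ijl, for school i, period j and adolescent l. Its random parts are u_i, the "random effect for cluster", and a residual e_ijl with a single variance and no stated covariance. X may be coded 0/1 or as a dose, and 3.1.3 defines dose at the level of the individual student.

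The paragraph before the equation lists, among the things a GLMM permits, "the specification of autocorrelation within individuals, and clustering by school". The text after it adds only that "SAS will be used if more complex specification of the intraclass correlation becomes necessary".

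The design follows a cohort. Section 2.3.2 plans "student surveys at baseline, 3, 9 and 12 months". Under Section 6, enrolled students must "agree to complete the survey at baseline and at 3, 9, and 12 months during and shortly after their cluster's program". Section 3.1.2 models dropout for each individual over the four occasions.

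**The concern.** The equation suits a stepped wedge that samples new students in each period. Here the same students return. When exposure is set by school and period, a student contributes surveys both before and after the school starts, so differences between students that persist over time cancel out of the comparison. A model without a student term leaves that variation in the residual and charges it to θ.

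At stake is whether the interval and test for the primary effect have their nominal coverage and size, and whether precision is given away in a trial with only five schools. There is also a specification problem. An analyst who follows the equation and one who follows the prose would fit different models, and the second would have to choose a structure that the plan does not name.

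**Working it through.** **Plan's own figure.** Section 3.1.1 gives Nu = 292, design effect 1.3273 and 15% attrition. 292 × 1.3273 = 387.6, so 388 completers; 387.57 / 0.85 = 455.97, so 456. The sample size reproduces.

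**Inputs.**
- From the documents: school ICC 0.016, effect 0.14, 5 schools in waves of 1, 2 and 2 (2.3.5), 4 surveys.
- Derived: 388 / 5 ≈ 78 students per school. Reading Nu as two groups of 146 tested two-sided at 5% with 80% power (sidedness is not stated), 0.14 = 2.80 × SD × √(2/146), so SD = 0.427.
- Assumed: r, the share of within-school variance that is stable between students, which equals the correlation between two surveys of one student in a school. The documents give no value.

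**1. Hand check of direction.** Compare baseline with the mean of three follow-ups in 388 students, without period effects.
- As written: SE = 0.427 × √((1 + 1/3)/388) = 0.0250.
- True SE = 0.0250 × √(1 − r) = 0.0209, 0.0177 and 0.0137 for r = 0.3, 0.5 and 0.7.
- Ratio = 1/√(1 − r) = 1.20, 1.41 and 1.83.

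**2. Stepped wedge with period effects.** Four periods, every school surveyed in every period, 78 per school. Let V be the school-mean covariance in the equation as written (school variance 0.016, independent residuals), and W the covariance with the student variance included. With A = ΣX′V⁻¹X and B = ΣX′V⁻¹WV⁻¹X, the reported variance is A⁻¹ and the true variance is A⁻¹BA⁻¹. The reported SE is 0.0944 SD, or 0.0944 × 0.427 = 0.0403. Type I error is 2Φ(−1.96 × ratio).

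| r | reported SE / true SE | type I error |
|---|---|---|
| 0.3 | 1.17 | 2.2% |
| 0.5 | 1.34 | 0.9% |
| 0.7 | 1.61 | 0.2% |

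**3. Variances re-estimated under the equation as written.** For r = 0.2, 0.4 and 0.6 the ratios are 1.11, 1.26 and 1.51. The reported SE is 0.095 SD throughout, against 0.085, 0.075 and 0.062 when a student effect is fitted. Simulated linear trials (REML, 1,500) gave 0.96, 1.17 and 1.42 at r = 0, 0.4 and 0.6, with null rejection of 6.4%, 2.3% and 0.9%.

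**4. Conditions that shrink or reverse the error.**
- Binary outcome (400 simulated trials per setting, logistic with school fixed effects): ratio 1.01, 1.09 and 1.22 at latent student ICC 0, 0.23 and 0.50; null rejection 5.0%, 3.0% and 2.2%.
- Half of student-visits contributing: ratio 1.04, 1.09 and 1.14 at r = 0.2, 0.4 and 0.6.
- Student-level dose as X: ratio 0.97, 0.93 and 0.91 at the same r, with type I error 5.9%, 6.7% and 7.6%. If the school variance is zero, the ratio falls as low as 0.84 and type I error reaches 10%.

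**5. Power for 0.14 with the equation as written.** On the step 2 inputs, power = Φ((0.14/0.0403 − 1.96) × ratio) = 96%, 98% and 99% at r = 0.3, 0.5 and 0.7. With half the students contributing (39 per school) it is about 74% to 80%.

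**The case against.** The strongest reply is that the equation is only a template. It is introduced as a form proposed in a cited methods paper, and it also lacks the logit link and covariates that the prose promises. The prose names "the specification of autocorrelation within individuals" separately from clustering by school, and it interprets log odds conditional on unobserved random effects. On this reading the fitted model would contain a student-level correlation. That is a fair account of likely intent, and it is why the point is one of reconciliation. It does not settle which model is primary: no term is written, and the software fallback is conditional and refers to the intraclass correlation.

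The reply is also right on size. The within-student correlation is not in the documents. The primary outcome is to be modelled as binary, and survey items 5.1 to 5.6 skip students who have never had intercourse and ask about the past month, so many student-visits may carry no condom-use proportion.

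A reader might infer that the 0.14 effect would often be missed. The documents do not support that. Figures such as 51% or 22% power arise only by choosing the effect at which a model with a student term has exactly 80% power. In step 1 that effect is 2.80 × 0.0177 ≈ 0.05 at r = 0.5 and 2.80 × 0.0137 ≈ 0.04 at r = 0.7, not 0.14. At 0.14, step 1 gives 0.14/0.0250 = 5.6 standard errors. Moreover, the sample-size formula in 3.1.1 contains no within-student correlation, so the planned 80% already belongs to a model without a student term.

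A reader might also infer that the standard error is always too wide. The dose coding that the plan allows is a counterexample.

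**Conclusion.** The point holds in a limited form. Taken literally, the equation omits a correlation that the design creates and the prose acknowledges, and the reported standard error is then miscalibrated. With 0/1 exposure the error is conservative: it does not create false positives, but it gives wider intervals than the data warrant. The linear-scale ratios of 1.17 to 1.61 rest on assumed correlations of 0.3 to 0.7 and on every school being surveyed in every period. Section 2.3.5 describes surveys at baseline and after each school's own start, so that second assumption may not hold; the before/after check does not need it and points the same way. For the binary primary outcome, or with sparse contributing visits, expect a smaller excess. This should be corrected before analysis, as a matter of specification and precision; it does not show that the trial is underpowered for its target.

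**What to change.** Write the primary model as Y_ijl = μ + β_j + θX_ij + u_i + v_il + e_ijl, where v_il is a random intercept for student l nested in school i. For condom use, apply a logit link to the same linear predictor and omit e_ijl. State that this is the primary specification and not a fallback, and amend the prose in 3.1.5 to match, so that the conditional software sentence covers only structures beyond the student intercept. The cost is one model term and a text change; no new data are needed.
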